#### **11.6.2 Immune Response for Secondary Endpoints**

Anti-Tau IgG, anti-pTau IgM and anti-Tau IgM titers, in serum, will be presented in the same way as antipTau IgG, outlined in section 11.6.1 above [TFL Shell Table 14.2.2.1, 14.2.2.1, 14.2.2.2, 14.2.2.2.1, 14.2.2.3, 14.2.2.3.1; 14.2.3.1, 14.2.3.1.1, 14.2.3.2, 14.2.3.2.1, 14.2.3.3, 14.2.3.3.1; 14.2.4.1, 14.2.4.1.1, 14.2.4.2, 14.2.4.2.1, 14.2.4.3, 14.2.4.3.1].

The anti-ePHF avidity index will be summarized by visit only [TFL Shell Table 14.2.6.1, 14.2.6.1.1].

The time-dependent development of the geometric mean titers (Anti-Tau IgG, Anti-pTau IgM, Anti-Tau IgM) and anti-ePHF avidity index will be displayed graphically per Treatment Group for the actual values as well as for change from baseline [TFL Shell Figure 14.1.2.1, 14.1.2.1.1, 14.1.2.1.2; 14.1.3.1, 14.1.3.1.1; 14.1.3.1.2; 14.1.4.1, 14.1.4.1.2; 14.1.6.1, 14.1.6.1.1; 14.1.6.1.2] and by subject [TFL Shell Figure 14.1.2.2; 14.1.3.2; 14.1.3.2; 14.1.4.2; 14.1.6.2]. Boxplot of the actual value summarized by Visit and Treatment Group will also be prepared [TFL Shell Figure 14.1.2.4; 14.1.3.4; 14.1.4.4] (not required for anti-ePHF avidity index).

Response rates by visit will be displayed graphically in a response rate verses dose plot to investigate whether there is any dose response relationship [TFL Shell Figure 14.1.2.3; 14.1.3.3; 14.1.4.3]. Response rates by visit are not applicable for the avidity index.

Key antibody ratios Anti-ePHF IgG / Anti-pTau IgG, Anti-ePHF IgG / Anti-Tau IgG and Anti-pTau IgG / Anti-Tau IgG will also be summarized by Treatment Group and Visit and presented graphically including Geometric Mean (±95% CI) over time by Treatment Group and subjects profile of the change from baseline of the log10 values [TFL Shell Table 14.2.9.4, 14.2.9.4.1, TFL Shell Figure 14.1.10.1, 14.1.10.2].

The Immunogenicity data will be also listed for the ITT Population [TFL Shell Listing 16.2.12.1 16.2.12.2, 16.2.12.3 and 16.2.12.4].

#### 11.6.3 Immune Response for Exploratory Endpoints

Anti-T50, anti-CpG and anti-CRM lgG titers in serum will be presented in the same way as outlined in section 11.6.1 above [TFL Shell Table 14.2.7.1, 14.2.7.1.1, 14.2.7.2, 14.2.7.2.1, 14.2.7.3, 14.2.7.3.1; 14.2.8.1, 14.2.8.1, 14.2.8.2, 14.2.8.2.1, 14.2.8.3, 14.2.8.3.1; 14.2.9.1, 14.2.9.1, 14.2.9.2, 14.2.9.2.1, 14.2.9.3, 14.2.9.3, 14.2.9.3.1]

The time-dependent development of the geometric mean titers (Anti-T50, anti-CRM and anti-CpG) will be displayed graphically per Treatment Group for the actual values as well as for change from baseline [TFL Shell Figure 14.1.7.1, 14.1.7.1.2; 14.1.8.1, 14.1.8.1.1, 14.1.8.1.2; 14.1.9.1, 14.1.9.1.1, 14.1.9.1.2] and by subject [TFL Shell Figure 14.1.7.2; 14.1.8.2; 14.1.9.2].

Response rates by visit will be displayed graphically in a response rate verses dose plot to investigate whether there is any dose response relationship [TFL Shell Figure 14.1.7.3; 14.1.8.3; 14.1.9.3].

### 11.7 Other Exploratory Analyses

[figure not shown]
#### 11.7.1 AD biomarkers in blood and CSF

The following putative AD biomarkers will be assessed in plasma:

- Brain-derived Tau (BD-Tau)
- pTau217+
- pTau181
- Aβ40
- Aβ42
- Aβ42/Aβ40 ratio
- NFL
- GFAP
- YKL-40

and in Cerebrospinal Fluid (CSF):

- pTau217+
- pTau181
- Total Tau
- Aβ40
- Aβ42
- Aβ42/Aβ40 ratio
- NFL
- GFAP
- Neurogranin
- YKL-40
- In a mass spectrometry assay not validated: pTauS396, pTauS199, pTauS202, pTauT205, pTauT231, pTauT217, pTauT181. All these biomarkers should be considered as purely exploratory, included pTau181 and pTau217 which have been tested with a validated assay (see above).

Blood samples for AD biomarker testing will be collected at all visits except screening [Visit 1 (Week 0), Visit 2 (Week 2), Visit 3 (Week 8), Visit 4 (Week 10), Visit 4.1 (Week 15), Visit 4.2 (Week 20), Visit 5 (Week 24), Visit 6 (Week 26), Visit 6.1 (Week 31), Visit 7 (Week 36), Visit 7.1 (Week 42), Visit 8 (Week 48), Visit 9 (Week 50), Follow-up Visit 10 (Week 67) and Follow-up Visit 11 (Week 74)].

CSF samples for AD biomarker testing will be collected at Screening, Visit 6 (Week 26) and Visit 9 (Week 50).

All AD biomarkers data, change from baseline, percent (%) change from baseline and fold-change from baseline will be summarized by Visit and Treatment Group for each source (plasma and CSF) [TFL Shell Table 14.2.10.1.1, 14.2.10.1.1, 14.2.10.2, 14.2.10.2.1]. AD Biomarkers (in CSF) for eligibility are summarized separately [TFL Shell Table 14.2.10.1.2.2, 14.2.10.2.3].

Each biomarker will be presented graphically in a time series plot, presenting mean values per Treatment Group, and in a box plot per Visit and Treatment Group for each source (plasma and CSF) [TFL Shell Figure 14.2.1, 14.2.2, 14.2.9, 14.2.10]. Individual data by subject will be displayed graphically by treatment group [TFL Shell Figure 14.2.3, 14.2.4]. Mean time course of change from baseline and individual change from baseline will also be provided [TFL Shell Figure 14.2.5, 14.2.6, 14.2.7, 14.2.8]. Box plots of actual log10-transformed values, fold-change from baseline and change from baseline of the log10-transformed values will be shown [TFL Shell Figure 14.2.11, 14.2.12, 14.2.13, 14.2.14, 14.2.15, 14.2.16].

The AD biomarker data in blood and CSF will be also listed for the ITT Population [TFL Shell Listing 16.2.13].

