## 6.1 Sample Size Considerations

Antibody titer assessment: The preliminary assessment of the antibody response and of the safety/tolerability (comparison between sub-cohorts) will be performed based on the data of all randomized subjects (6 on ACI-35.030/JACI-35.054 and 2 on placebo per sub-cohort) based on the timepoints related to the different IAs that will be conducted during the study. The initial number of subjects in each sub-cohort is consistent with the customary sample size employed in this type of studies. It is expected to allow clinical judgement of safety and tolerability, and to get preliminary evidence of an acceptable immune response. This sample size is also anticipated to provide sufficient evidence to support the possible enrollment of up to 16 additional subjects in the sub-cohort(s) showing the most favorable antibody response profile(s) with the objective to confirm the initial results. The number of additional subjects to be enrolled will be determined based on the preliminary observed immunogenicity response rate in the subcohort(s), and on the potential gain in precision of the response rate estimate in the expanded sub-cohort(s), and will not exceed 16 (12 on ACI-35.030/JACI-35.054 and 4 on placebo per sub-cohort). In addition, all other immunogenicity endpoints available at the interim timepoint may be considered in the sample size re-estimation. This may include but is not limited to the observed variability of titers such as the Anti-pTau IgG and the Anti-e-PHF IgG.

In total, up to 24 subjects can be randomized to cohort 1, cohort 2 and cohort 3, respectively (not taking into account sub-cohort(s) expansion). Any randomized subject withdrawing before the 2nd injection for reasons other than safety may be replaced in the cohort.

For safety, if an AE occurs at the rate of 1% or 10%, then the chance of observing such an AE among 6 subjects receiving that dose of active treatment will be 6% or 47%, respectively. If no AE of a given type is observed in any of the 6 subjects at a given dose of active treatment, then with 80% (90%) confidence the true incidence of that type of AE at that dose is at most 24% (32%).

An expansion was done in sub-cohort 1.2 in which 17 additional subjects were recruited (for a total of 25 subject in the sub-cohort) to allow further assessment of safety and immunogenicity at that dose.

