## 8.3 Change from Baseline

The change from baseline value is defined as the value at any given post-baseline timepoint minus the baseline value, i.e. post-baseline value – baseline value.

Percent change from baseline is defined as follows: ((post-baseline value – baseline value) / baseline value) \* 100.

Fold-change from baseline is defined as the ratio calculated by the post-baseline value divided by the baseline value. A value of 1 indicates a post-baseline value equal to the baseline value. A value above 1 indicates an increase from baseline; a value below 1 indicates a decrease from baseline.

[figure not shown]

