# 11.0 Statistical Methods

All analyses will use SAS® version 9.4 or higher. Descriptive summaries will be tabulated by treatment group (ACI 300µg, ACI 900µg, ACI 1800µg, JACI 15µg, JACI 60µg). Where applicable, all subjects from each main cohort will be summarized together (excluding immunogenicity and biomarker TFLs).

Categorical data will be presented using counts and percentages, with the number of subjects in each category as the denominator for percentages. Percentages will be rounded to one decimal place except 100% will be displayed without any decimal places and percentages will not be displayed for zero counts.

Continuous data will be summarized using the number of observations (n), mean, standard deviation (SD), median, first quartile, third quartile, minimum, and maximum. Minimum and maximum will be rounded to the precision of the original data. Mean and median will be rounded to 1 decimal place greater than the precision of the original data. The SD will be rounded to 2 decimal places greater than the precision of the original data, up to a maximum of 3 decimal places.

A sensitivity analysis may be carried out at the end of the study if the number of patients impacted by the COVID-19 pandemic is large (e.g. >10% missed injections due to COVID-19) and thought to be impacting the efficacy and safety endpoints. This sensitivity analysis may exclude the patients affected by the pandemic.

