#### **11.6.1 Immune Response for Primary Endpoints**

Descriptive statistics of actual values and changes from baseline as outlined in section 11.0, with the addition of Geometric Mean and 95% normal approximation confidence intervals (CI) as outlined in sections 8.15 and 8.17, will be presented for the primary immune response variable, anti-pTau IgG and anti-ePHF IgG titers in serum by Visit [Baseline, Visit 2 (Week 2), Visit 3 (Week 8), Visit 4 (Week 10), Visit 4.1 (Week 15), Visit 4.2 (Week 20), Visit 5 (Week 24), Visit 6 (Week 26), Visit 6.1 (Week 31), Visit 7 (Week 36), Visit 7.1 (Week 42), Visit 8 (Week 48), Visit 9 (Week 50), Follow-up Visit 10 (Week 67) and Follow-up Visit 11 (Week 74)] and Treatment Group [TFL Shell Table 14.2.1.1, 14.2.1.1.1; 14.2.5.1, 14.2.5.1.1]. This variable will further be summarized by Treatment Group for responder rate [TFL Shell Table 14.2.1.2, 14.2.1.2.1; 14.2.5.2, 14.2.5.2.1], and area under the curve and peak [TFL Shell Table 14.2.1.3, 14.2.1.3.1; 14.2.5.3, 14.2.5.3.1] by Treatment Group (and overall for baseline data only) in the Intention-to-Treat Population.

The time-dependent development of the geometric mean titers will be displayed graphically per Treatment Group for the actual values as well as for change from baseline [TFL Shell Figure 14.1.1.1, 14.1.1.1.2; 14.1.5.1, 14.1.5.1.1, 14.1.5.1.2] and by subject [TFL Shell Figure 14.1.1.2, 14.1.5.2]. Boxplot of the actual value summarized by Visit and Treatment Group will also be prepared [TFL Shell Figure 14.1.1.4 and 14.1.5.4].

Response rates by Visit will be displayed graphically in a response rate verses dose plot to investigate whether there is any dose response relationship [TFL Shell Figure 14.1.1.3; 14.1.5.3].

No statistical testing has been planned for antibody responses.

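### The default arithmetic mean of biomarker fold-change and percent change is biased upward for a within-group reading; a geometric mean fold-change should replace it

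*SAP*

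**What the plan says.** SAP 8.3 defines both quantities subject by subject. For the ratio, "Fold-change from baseline is defined as the ratio calculated by the post-baseline value divided by the baseline value". Percent change is the difference from baseline divided by baseline, times 100, which equals 100 × (fold-change − 1).

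SAP 11.7.1 then states that "All AD biomarkers data, change from baseline, percent (%) change from baseline and fold-change from baseline will be summarized by Visit and Treatment Group", for plasma and CSF separately, without naming a summary statistic. The general rule in SAP 11.0 fills the gap: "Continuous data will be summarized using the number of observations (n), mean, standard deviation (SD), median, first quartile, third quartile, minimum, and maximum".

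Elsewhere the SAP names a geometric mean where it wants one: for antibody titers (11.6.1), key antibody ratios (11.6.2) and volumetric MRI (11.7.4). It names none for the AD biomarkers. It does plan graphical output on the log scale: "Box plots of actual log10-transformed values, fold-change from baseline and change from baseline of the log10-transformed values will be shown". The biomarker time-series plots are described as "presenting mean values per Treatment Group". Mean time courses are specified for actual values and for change from baseline, but not for fold-change or percent change.

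**The concern.** Ratios are not symmetric about 1. A subject who doubles contributes +1.00 to the average and a subject who halves contributes −0.50, so one of each gives a mean fold-change of 1.25, or +25%, with no net change on the log scale. Inverting every ratio would give the same apparent rise.

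Protocol 1.4 treats the effect on total Tau and pTau as preliminary evidence of epitope engagement. With few subjects and no model or test, the descriptive statistics are the result. If the mean in the biomarker tables is read against 1 (or 0%), a real fall can look smaller than it is, or disappear, and the mean and median in one row can point in different directions.

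**Working it through.** The plan gives no biomarker effect size, SD or power, so there is no figure of its own to reproduce on this point.

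**Inputs**
- Fold-change is post-baseline over baseline for each subject (SAP 8.3).
- Biomarker baseline is one value, the last non-missing value before the first injection (SAP 8.2; averaging applies only to titers). Each ratio therefore carries the noise of two measurements.
- Initial group size: "6 on ACI-35.030/JACI-35.054 and 2 on placebo per sub-cohort" (SAP 6.1). Sub-cohort 1.2 reached 25 subjects; about 18 active is assumed from the 3:1 ratio.
- Assumed, not documented: log-normal measurements with within-subject SD s per measurement (natural-log scale), s = 0.1 to 0.4, and an illustrative true fall of 10%.

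**Expected mean.** With true ratio g, ln(ratio) is normal with mean ln g and variance 2s². The expected arithmetic mean fold-change is g × exp(2s²/2) = g × exp(s²). The geometric mean has no such factor on the log scale, so it centres on g.

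- No change (g = 1): exp(0.01) = 1.010, exp(0.04) = 1.041, exp(0.09) = 1.094, exp(0.16) = 1.174.
- True 10% fall (g = 0.90): 0.909, 0.937, 0.985, 1.056, shown as −9%, −6%, −2% and +6%.
- Largest true fall fully offset in expectation, 1 − exp(−s²): 1.0%, 3.9%, 8.6%, 14.8%.

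**How often a group of 6 shows no fall when the truth is a 10% fall.** For the geometric mean this is exact: Φ(ln 0.90 × √6 / (s√2)). At s = 0.2, that is Φ(−0.1054 × 2.449 / 0.2828) = Φ(−0.91) = 18%. The arithmetic mean and median were simulated with 400,000 groups.

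| s | arithmetic mean ≥ 1 | geometric mean ≥ 1 | median ≥ 1 |
|---|---|---|---|
| 0.1 | 5% | 3% | 5% |
| 0.2 | 27% | 18% | 22% |
| 0.3 | 43% | 27% | 31% |
| 0.4 | 54% | 32% | 36% |

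A larger group does not remove the bias. At n = 18 and s = 0.2, 0.3, 0.4, the arithmetic mean shows no fall in 16%, 42% and 62% of groups, against 6%, 15% and 21% for the geometric mean.

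**Disagreement within one row.** Five subjects at 0.70 and one at 2.50 give an arithmetic mean of (5 × 0.70 + 2.50)/6 = 1.00, a geometric mean of 0.87 and a median of 0.70.

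**Contrast with placebo.** With equal s in both arms, both means are multiplied by exp(s²) and the ratio of expected means stays at 0.90. Simulating 6 active against 10 placebo (assumed: 2 from each of five initial sub-cohorts, pooled), the active arm fails to look lower in 23%, 31% and 35% of trials with arithmetic means and 24%, 32% and 36% with geometric means (s = 0.2, 0.3, 0.4). The choice of mean makes almost no difference to that comparison.

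**The case against.** The strongest reply is that the outputs as a whole are not misleading.

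- The SAP 11.0 rule that supplies the mean also supplies the median and quartiles, and the table above shows the median close to the geometric mean. Log10-change box plots, individual profiles and listings are planned too. This stands: a reader might infer that the plan conceals a fall in pTau, and the documents do not support that.
- The trial is placebo-controlled, and an equally variable placebo arm carries the same inflation. This stands under equal spread. It weakens if response to vaccine varies between subjects: with an assumed extra log-SD of 0.3 in the active arm only, a true ratio of 0.90 would appear as 0.90 × exp(0.09/2) = 0.94. With 2 placebo subjects per initial sub-cohort, change within an active group is also likely to be read on its own.
- The size is unknown because no biomarker variability is documented. This stands: at s = 0.1 the bias is 1% and unimportant. Nor do the documents show that noise differs enough between analytes to make them non-comparable.
- The table shells are in a separate document that is not available here, and the SAP history for version 4.0 records changes to summary statistics. A geometric mean may already be in the shells. This stands: the arithmetic mean is what the SAP text implies, not a verified feature of the tables.
- One might extend the argument to Figures 14.2.5 and 14.2.6. It does not carry over: they show post-baseline minus baseline, which has expectation zero under no change.

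**Conclusion.** The point holds as a limited one. As the SAP reads, the mean fold-change and mean percent change for biomarkers are arithmetic and, read within a group against no change, too high in expectation by a factor exp(s²): +1% to +17% for s from 0.1 to 0.4. At s = 0.3 or more this is as large as a fall of about 9% or more. The bias is a property of the expectation; not every sample with no true change will show a rise.

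The size rests on log-normal data, a single baseline value and assumed values of s. The mechanism does not depend on the exact value. Severity is low: the endpoint is exploratory and descriptive, no test or decision threshold depends on this mean, and the median, the log-scale plots and (with equal spread) the placebo comparison remain sound.

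**What to change.** In SAP 11.7.1, state that fold-change will be summarized by the geometric mean fold-change, the antilog of the mean log10 change from baseline, with a back-transformed 95% confidence interval. State that percent change will be reported as 100 × (geometric mean fold-change − 1). These replace the arithmetic means of the two ratios in the biomarker change tables (the 14.2.10.1.x series, apart from the eligibility tables, which show actual values only). Keep the median and quartiles. Leave Figures 14.2.5 and 14.2.6 as they are.

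The cost is one or two sentences and a change of summary statistic in the shells, if they do not already have it. The log10 changes are already derived for Figures 14.2.15 and 14.2.16, and the result would match the SAP's handling of titers and antibody ratios.

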#### 11.7.2 T-cell activation (ELISPOT)

T-cell activation (as measured by the ELISPOT assay) will not be tested for this study since there is no safety concern. No outputs on T-cell activation will be prepared.

#### 11.7.3 Inflammatory cytokines in blood

[figure not shown]
Inflammatory cytokines (e.g. IL-1 $\beta$ , IL-2, IL-6; IL-8, IL-10, IFN- $\gamma$  and TNF- $\alpha$ ) will not be tested for this study since there is no safety concern. No outputs on inflammatory cytokines in blood will be prepared.

#### 11.7.4 Volumetric MRI

Volumetric MRI analyses will also be performed by **Example 1** The volume of different brain regions (i.e. whole brain, intracranial, hippocampus and ventricles) will be measured at screening (baseline) using an automated FreeSurfer-based segmentation method. An automated Tensor-Based Morphometry (TBM) method will then be used to measure the change of volume at follow-up visits for each of the following structures:

- whole brain (bilateral)
- hippocampus (bilateral, left and right)
- ventricles (bilateral)

For each brain structure, volume change at follow-up visits [Visit 4 (Week 10), Visit 6 (Week 26), Visit 9 (Week 50) and Visit 11 (Week 74)] will be presented graphically in a time series plot, presenting mean values (CI 95%) per treatment group [**TFL Shell Figure 14.5.2**] and individual values [**TFL Shell Figure 14.5.3**]. Box plot of MRI volume by brain region, visit and treatment group will also be presented [**TFL Shell Figure 14.5.4**]. Baseline data and volume change at each follow-up visit data will be summarized

per treatment group [**TFL Shell Table 14.3.8.3**] for each structure. Geometric mean, standard deviation, median, 25th quantile, 75th quantile, minimum and maximum will be reported. Individual baseline values and volume change at each follow-up visit will also be presented [**TFL Shell Listing 16.2.7.7.2**].

## 12.0 Changes from the Analysis Planned in the Protocol

Due to the COVID-19 pandemic a notification of an Urgent Safety Measure (USM) for a change to protocol study procedures, effective immediately, was submitted to FIMEA on **01-Apr-2020** and Finnish EC (TUKIJA) on **03-Apr-2020**. A protocol amendment following the USM including the below changes was submitted to FIMEA on **17-Apr-2020** and TUKIJA on **24-Apr-2020**:

- Replacement of Visit 5 (Week 24) and Visit 6 (Week 26) by remote visits in 7 of 8 Sub-cohort 1.1 subjects. As a consequence, the third immunization, as well as procedures and assessments requiring the subjects to travel at Visit 5 (Week 24) and Visit 6 (Week 26) were cancelled.
- Cancellation of the third phone call (P3), usually performed 48-72 hours after the third immunization. This change is impacting 7 of 8 subjects who have not had their immunization at Visit 5 (Week 24) prior to the at-risk period.

Due to the changes presented above IA #2 Sub-cohort 1.1 at Week 50 will be executed as follows:

- Individual data (listings and individual figures) will not be presented for IA #2 Sub-cohort 1.1 Week 50.
- Aggregate data (summary tables and figures) will be provided for all timepoints (up to Week 50) except the timepoints where the visits were missed by 7 of 8 subjects in Sub-cohort 1.1 for which we will have only 1 value (i.e. Visit 5 Week 24 and Visit 6 Week 26).

Footnotes will be included to all outputs affected by the selection criteria as given below:

• Aggregate data outputs: "Note: Aggregate data is provided for all visits except those missed by 7 out of 8 subjects in Sub-cohort 1.1 (Visits 5 and 6)."

In certain cases, where subjects missed any visit or dropped out from the study, IA will be executed as follows:

[figure not shown]
- If there is a risk of unblinding individual data (listings and individual figures) will be presented only up until the missed visit or data for those subjects will not be included.
- Aggregate data (summary tables and figures) will be provided for all timepoints

### 13.0 Validation

goal is to ensure that each TFL delivery is submitted to the highest level of quality. quality control procedures will be documented separately in the study specific quality control plan.

[figure not shown]
# **Appendix 1 Glossary of Abbreviations**

AD	Alzheimer's Disease
AE	Adverse Event
ANA	Anti-nuclear Antibodies
Anti-dsDNA	Anti-double stranded DNA Antibodies
АроЕ	Apolipoprotein E
aPTT	activated Partial Thromboplastin Time
AUC	Area Under the Curve
BLQ	Below the Limit of Quantification
CDR-SB	Clinical Dementia Rating scale Sum of Boxes
CI	Confidence Interval
cm (unit)	Centimeter
CRF	Case Report Form
CRP	C-Reactive Protein
CSF	Cerebrospinal Fluid
C-SSRS	Columbia-Suicide Severity Rating Scale
DLP	Data Lock Point
DSMB	Data and Safety Monitoring Board
ECG	Electrocardiogram
EDC	Electronic Data Capture
ELISPOT	Enzyme-Linked Immunospot
ePHF	Enriched Paired Helical Filament
Gamma-GT	Gamma-glutamyl Transferase
IA	Interim Analysis(ses)
ID	Identifier / Identification Number
IFN-γ	Interferon-gamma
lgG	Immunoglobulin G
IL-4	Interleukin-4
IMP	Investigational Medicinal Product
INR	International Normalized Ratio
IRT	Interactive Response Technology
ITT	Intention To Treat
kg (unit)	Kilogram
LLOQ	Lower Limit of Quantification

Statistical Analysis Plan

μg (unit)	Microgram
MacCAT-CR	MacArthur Competence Assessment Tool for Clinical Research
MCI	Mild Cognitive Impairment
MMSE	Mini Mental State Examination
MRI	Magnetic Resonance Imaging
NPI	Neuropsychiatric Inventory Scale
PBS	Phosphate Buffered Saline
PP	Per Protocol
PSO	Predictivv Study Operation
рТаи	Phospho-Tau
RBANS	Repeatable Battery for the Assessment of Neuropsychological Status
SAE	Serious Adverse Event
SAP	Statistical Analysis Plan
SD	Standard Deviation
SDRC	Sponsor Data Review Committee
SUSAR	Suspected Unexpected Serious Adverse Reaction
TEAE	Treatment Emergent Adverse Event
USM	Urgent Safety Measure
eTMF	electronic Trial Master File
ТВМ	Tensor-Based Morphometry
TNF-α	Tumor Necrosis Factor alpha

